**ANNEX 1-FINAL NOVARTIS APPROVED PROTOCOL FOR THE STUDY**

## Investigator Initiated Trial

**(1) Title of study**

Effects of Ranibizumab to delay or regression non-proliferative diabetic retinopathy(NPDR) with DME assessed by microaneurysm changes: A pilot study

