**(4) Study Design**

single center, prospective, interventional, one arm, pilot study

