**(5) Objectives**

**Objectives:** To evaluate the effects of intravitreal Ranibizumab injection on microvascular changes in eyes of mild-to-moderate NPDR with DME.

**Primary objective:** To compare microvascular changes assessed by microaneurysm counts in eyes of mild-to-moderate NPDR with DME after intravitreal Ranibizumab injection from baseline through 6 months after treatment.

**Secondary objectives:** To investigate other efficacy endpoints including other microvascular, anatomical, visual acuity change and safety in mild-to-moderate NPDR with DME after intravitreal Ranibizumab injection from baseline through 6 months after treatment.

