Kohner and Sleightholm^13 describe this concept at first time in 1986, its association with the number of microvascular flow and the severity of diabetic retinopathy. In recent years it is reported that measuring the number of microaneurysm and the turnover rate associated with the appearance or disappearance of microaneurysm, are predictors in progression of diabetic retinopathy and macular edema.

To delay the progression of diabetic retinopathy and to improve macular edema, the laser photocoagulation have been the important role. Although the laser photocoagulation have had treatment effect in the diabetic retinopathy by reducing the amount of VEGF in micraneurysm and by degenerating the neovascularization after laser therapy, there was a problem that has many limitations - peripheral visual field defects, night blindness, progression of macular edema etc., and that the disease does not cured in a good time because of limits of laser therapy due to cataract, vitreous hemorrhage and turbidity. As an alternative method to solve these limitations, there is an anti-VEGF therapy. According to a previous study result, intraocular injection of Bevacizumab inhibits occurring of neovascularization by blocking the VEGF receptor .

Recently, several studies have been reported that when injected intravitreal anti-VEGF, macular edema is improved and neovascularization is inhibited, by reducing the leakage of neovascularization.

Especially, Leicht SF et al reported the number of microaneurysms and turnover rate in NPDR(non-proliferative diabetic retinopathy) patients injected with Ranibizumab. And the result showed entire number of the microaneurysms and turnover rate are decreased, which could be mean the regression of diabetic retinopathy and it could decide the therapeutic effect.

On this study, through the fluorescein fundus angiography, the average number of microaneurysms was significantly decreased after intravitreal injection of anti-VEGF therapy ( $p < 0.05$ ). The decrease of  $35.70 \pm 24.79\%$  in the treatment group was statistically higher than  $13.95 \pm 38.21\%$  in the control group of the fellow eye ( $p < 0.05$ ).

The result is found because decreased concentration of intravitreal VEGF inhibits the progression of diabetic retinopathy, such as endothelial cell proliferation and endothelial cell damage on retinal capillary and perivascular cells.

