Sjølie AK et al reported up-regulation of VEGF occurring microaneurysms causes endothelial cell proliferation and inflammation and effusion reaction, so anti-VEGF is effective in early diabetic retinopathy. But there is less effectiveness in late diabetic retinopathy as it reaches the non-changing point. Also Kohner EM et al reported diabetic retinopathy lesions are reversible and could be delayed in early diabetic retinopathy.

So far, changes of microaneurysms in late diabetic retinopathy is uncertain, and if there would be a finding according to anti-VEGF therapy, we could get a clue of surrogate marker which represents treatment results in diabetic retinopathy.

This study was designed to find the clinical evaluation and reduction rate through fluorescein angiography as microaneurysm examination tools to research NPDR with DME treatment results assessed by microaneurysm counts, timely monitored with anti-VEGF therapy.

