### **Statistical Analysis Plan**

Result analysis The investigators compare the differences between at baseline, at 3 month, and at 6 month. Statistical analyses will be performed using SPSS ver.18.0 (SPSS Inc., Chicago, IL, USA). Kolmogorov-Smirnov test was applied to test for normality of sample group data. The repeated measures analysis of variance with Bonferroni correction was used to analyze continuous outcome measures, including BCVA, CRT, total number of MAs, MA formation rate, MA disappearance rate, MA turnover, and perifoveal non-perfused area, before and after completion of 6 months of IVR therapy. A P-value <0.05 was considered statistically significant.

Table 1. Schedule of visits and procedures

Note: X = procedure to be performed, R = rescue treatment	Baseline Month 0 (Visit 1)	Month 1 (Visit 2)	Month 2 (Visit 3)	Month 3 (Visit 4)	Month 4 (Visit 5)	Month 5 (Visit 6)	Month 6 (Visit 7)
Informed consent	X						
Review eligibility criteria	X						
Demographics	X						
ETDRS BCVA	X	X	X	X	X	X	X
Slit lamp exam	X	X	X	X	X	X	X
IOP	X	X	X	X	X	X	X
OCT	X	X	X	X	X	X	X
Color Fundus Photo	X	X	X	X	X	X	X
FA	X			X			X
ICGA	X			X			X
Lucentis® injection	X	X	X	X	X	X	
Adverse events	X	X	X	X	X	X	X

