**(11) Statistics**

We compare the differences between at baseline, at 3 month, and at 6 month. Statistical analyses will be performed using SPSS ver.12.0 (SPSS Inc., Chicago, IL, USA). The Wilcoxon signed rank test will be examined for timely changes in microvascular change (microaneurysm, non-perfusion area, cotton wool spot & hard exudate)

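### Must the SAP of this one-arm pilot state in advance that its before/after tests on microaneurysm count do not measure the effect of ranibizumab?

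*Combined protocol and SAP*

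**What the plan says.** Section (4) Study Design describes a "single center, prospective, interventional, one arm, pilot study", and section (10) Methodology repeats this. The title reads "Effects of Ranibizumab to delay or regression non-proliferative diabetic retinopathy(NPDR) with DME assessed by microaneurysm changes" and ends by calling the trial a pilot. The general objective in section (5) is "To evaluate the effects of intravitreal Ranibizumab injection on microvascular changes". The primary objective in the same section is narrower: a comparison of MA counts from baseline through 6 months after treatment. Section (6) Study rationale hopes that "we could get a clue of surrogate marker which represents treatment results in diabetic retinopathy".

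Two texts describe the analysis, and both compare baseline, month 3 and month 6:
- The Statistical Analysis Plan uses repeated-measures ANOVA with Bonferroni correction for all continuous outcomes, "before and after completion of 6 months of IVR therapy. A P-value <0.05 was considered statistically significant".
- Section (11) Statistics says: "The Wilcoxon signed rank test will be examined for timely changes in microvascular change".

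Neither text plans a comparator, an interval estimate or a statement on how far the conclusion may go.

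Section (6) also quotes background data obtained "through the fluorescein fundus angiography": a decrease in MAs of 35.70 ± 24.79% in treated eyes against 13.95 ± 38.21% "in the control group of the fellow eye".

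**The concern.** The title and general objective ask what ranibizumab does. The analysis asks only whether MA count differs from its baseline value. With one arm, a significant fall may be drug effect, natural turnover, measurement change, or a mixture of these. Section (6) itself says that MAs can close by clotting while new ones form elsewhere.

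The rationale sharpens the worry. Its argument for a treatment effect rests on treated eyes against control eyes, and the control eyes fell too. Taken at face value, the control fall is 39% of the treated fall (13.95/35.70), which leaves a difference of 21.75 points rather than 35.70. So zero cannot simply be assumed as the value without the drug. At stake is a report that reads P<0.05 against baseline as evidence that ranibizumab regresses retinopathy.

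**Working it through.** **What can be reproduced.** Nothing: section (7) gives 25 patients with no power, effect size or SD. The figures below only show how large the ambiguity could be.

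**Inputs.**
- n = 25, from section (7).
- Control-eye fall 13.95%, SD 38.21; treated-eye fall 35.70%, SD 24.79, from section (6). That ± means SD is an assumption.
- Two-sided alpha 0.05 (sidedness assumed), or 0.05/3 = 0.0167 for Bonferroni over three visit pairs.

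**Drift with no drug effect, percent scale.** Standard error = 38.21/√25 = 7.642. Noncentrality = 13.95/7.642 = 1.825. With 24 degrees of freedom the critical t is 2.064 at alpha 0.05 and 2.574 at 0.0167. The noncentral t distribution gives the chance of a significant fall:

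| Assumed drift | alpha 0.05 | alpha 0.0167 |
|---|---|---|
| 5% | 9% | 4% |
| 10% | 24% | 12% |
| 13.95% | 42% | 25% |
| 20% | 71% | 53% |

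A simulated Wilcoxon signed rank test at 13.95% gives 39% and 23%, so the choice between the two named tests matters little here. These figures are not type I errors of the planned test, whose null hypothesis is no change; under drift that null is false.

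**Count scale.** The planned outcome is the number of MAs, not percent change. Baseline counts were simulated as log-normal with mean 10 to 40 and coefficient of variation 0.5 to 1.0 (assumed; the documents give none). The month-6 count was baseline × (1 + a normal change with mean −13.95% and SD 38.21%), rounded and floored at zero. The chance of a significant fall is then 26% to 36% at 0.05 and 12% to 20% at 0.0167.

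**How firm is the 13.95%?** The 95% CI for the control mean is 13.95 ± t × 38.21/√n. For n = 25 this is 13.95 ± 15.77, or −1.82 to 29.72. It includes zero up to n = 31 (−0.07 to 27.97) and first excludes it at n = 32 (0.17 to 27.73). Section (6) gives no n, no follow-up time and no statement that the control eyes were untreated. Those counts came from angiography, whereas section (10) counts MAs on fundus photographs with Retmarker. The figure cannot fix the drift in this trial.

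**What would an interval add?** If the treated-eye result recurred with n = 25, the half-width would be 2.064 × 24.79/5 = 10.2 points, so a fall of 35.7% (95% CI 25.5% to 45.9%). This is useful in a report, but it is still an interval for change from baseline and does not supply the missing control.

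**What would a fellow-eye comparison add?** The SD of the paired difference is √(24.79² + 38.21² − 2r × 24.79 × 38.21), which is 45.55 for r = 0 and 33.58 for r = 0.5. With 25 pairs the 95% half-width is 18.8 or 13.9 points. The documents do not say that fellow eyes are photographed or left untreated, and such eyes need not meet the entry criterion on retinal thickness. The comparison may not be possible and would not be like for like.

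**The case for a change.** The case for a change is that it costs almost nothing: one sentence and one table row, with no extra patients or visits. A pilot's most useful product is an estimate with its uncertainty, yet the plan ends on a bare P<0.05. The word pilot in the title does not limit what is claimed, and a title about effects invites a causal reading. The rationale's own control eyes give a specific reason for care, beyond the general weakness of one-arm trials.

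The statistical part of this stands: the tests show change over time and no more. It does not follow that the plan has to be amended. The primary objective, the endpoints and both analysis texts are all worded as change from baseline, so the tests match the stated comparison. No passage sets a rule that turns P<0.05 into a claim of drug effect. How a result is described belongs mainly to the report.

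The remedy also has no natural stopping point at MA count. Section (10) lists best corrected visual acuity and central macular thickness as the primary endpoints, and the same limit on attribution applies to them. A caveat on MA count alone would leave those P-values without one. No background control figure is needed to justify the caveat for any outcome.

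**Conclusion.** No change to the plan is needed. Within-patient change is what a one-arm trial can show. The protocol declares that design, words its primary objective to match, and states no number, rule or test that is wrong on this point. The missing interval and caution are details that a competent analyst supplies when reporting: change from baseline with a 95% CI for every efficacy outcome, described as change over time.

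The possible size of misattribution is not trivial: 12% to 42% across the scales and alpha levels shown if the drift were 13.95%. But it depends almost wholly on that drift. On percent change it runs from 4% (drift 5%, alpha 0.0167) to 71% (drift 20%, alpha 0.05). The source of the 13.95% has no stated n, follow-up or treatment status and used a different imaging method, so it serves as a caution and not as a benchmark. The conclusion rests on reading ± as an SD for the figures, and on the report keeping to the before/after wording of the primary objective. The different tests named in the two analysis texts, and the listing of MA count as primary in section (5) but secondary in section (10), are separate matters; this conclusion holds whichever way they are settled.

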**(11) Statistics**

We compare the differences between at baseline, at 3 month, and at 6 month. Statistical analyses will be performed using SPSS ver.12.0 (SPSS Inc., Chicago, IL, USA). The Wilcoxon signed rank test will be examined for timely changes in microvascular change (microaneurysm, non-perfusion area, cotton wool spot & hard exudate)

## ANNEX 3- PAYMENT PLAN

The agreed Study budget for the clinical trial is a maximum amount of (79,063,000 KRW (VAT excluded))

The payments will be due and transferred to the Sponsor in accordance the following milestones:

1. 10%(maximum) for study start up activities
  - a. (max of 5%) upon Agreement execution and Novartis approval of protocol
  - b. (rest of the initial 10%) upon IRB/EC/HA final approved protocol & FPFV
2. 30% of total agreement at 10% recruitment
3. 20% of total agreement at 50% recruitment
4. 20% of total agreement at 100% recruitment
5. 10% of total contract at provision of the final study report (TPSR)
6. 10% of the total contract at receipt by Novartis of the final publication or confirmation of publication submission (including but not limited to: congress abstracts, posters, oral presentation or journal publication, hereinafter the same).

However, if the final publication or confirmation of publication submission is provided between twenty-four (24) and thirty-six (36) months from LPLV, only 5% of total contract will be paid. If the final publication or confirmation of publication submission is not provided within thirty-six (36) months from LPLV, the Sponsor shall pay to Novartis 10% of total contract as a penalty.

#### **ANNEX 4- DRUG SUPPLY ACTIVITIES/ RESPONSIBILITIES**

Prior to any Study Drug shipment, the Sponsor shall provide Novartis with the public registration number of the Study. Provided the Sponsor has given Novartis the study number which is registered with the health authorities and a copy of the approvals from the appropriate health authorities and ethics committees, Novartis shall supply the Sponsor with sufficient supplies of the Study Drug to conduct the entire Study.

Novartis shall bear the costs arising from the shipment of the Study Drug to the Participating Sites, including customs duties or VAT if applicable.

The Sponsor shall observe the standard requirements of Good Manufacturing Practices (GMP) for Investigational Medicinal Products.

The Sponsor will maintain records of the packaging and labeling (if applicable), receipt, storage, administration or dispensing, return and destruction of Study Drug, identifying (but not necessarily by name) each patient to whom the drug is administered or dispensed, and will make these records available to Novartis at any time with the patient details redacted so as to preserve the patients' anonymity. The Sponsor is responsible for labeling according to local laws and regulations. The Sponsor shall ensure that any shipment of Study Drug is inspected upon receipt. The Sponsor shall ensure that any notice of defect or non-conformity is sent to Novartis within ten (10) days from receipt of Study Drug. The failure to provide such notice shall be deemed an acceptance of Study Drug by the Sponsor or its Subcontractors. Latent defects which are detected later shall be immediately reported to Novartis for further processing within Novartis. Shipment of Study Drug may be withheld at any time for failure to promptly respond to requests for production of the Study Drug records. Upon completion or termination of the Study, the Sponsor shall follow Novartis' instructions regarding the return or disposal of all unused Study Drug. The Sponsor shall be responsible for compliance with all laws and regulations applicable to any destruction or disposal of Study Drug at Participating Sites. The Sponsor will follow the instructions of Novartis in case Novartis determines that a recall of the Study Drug is required and in addition, the Sponsor will inform Novartis should the Sponsor determine that a recall of the Study Drug is required.

The Sponsor will keep all Study Drug under appropriate storage conditions and in a secured area accessible only to authorised personnel. Exceptions to storage conditions should be reported to Novartis.

Without limiting the generality of the foregoing, Novartis may perform drug supply activities on behalf of the Sponsor as set forth in the table below:

**[Please choose between option A or B; option B is applicable for open label studies]**

		IIT Trials								
CATE-GORY	Activity/Responsibilities	Option A Supply of blinded Patient Packs by NVS (full support)				Option B Supply of Bulk/Primary packaged unlabeled Drug product by NVS				
		TRD	CP O	NVS QPs	Sponsor	TRD	CPO	NVS QPs	SupplyCRO*	Sponsor
IMP SUPPLY PROVISION of bulk DP	Supply of bulk IMPs ( fill-in, examples below ): Active Placebo Comparator Novartis Marketed Product (provided by CPO)	N/A	N/A	N/A	N/A	X X X	X			
	TRD QA Release of Drug Product (CofA)	X				X for TRD supplied DP				
IMP PACKAGING	Label design	X	X						X	X
	Provide information for labels (e.g., storage conditions)	X				X				
	IMP Label approval				X					X
	IMP Packaging and Labeling	X							X	
	Technical Release of final packaged IMP (CoC)	X						X	X	
IMP CERTIFICATION	QA Agreement between:			X	X			X	X	
	QP Batch certification of bulk/primary packed IMPs Step 1: Manufacturer applies GMPs equivalent to EU GMPs Step 2: Compliance with Product Specification File for bulk IMP (CoA level) Step 3: Compliance with approved Quality Part of IMPD for bulk IMPs (CoA level), per EU country			X				X		

\* Assumption: CRO is located in EU, participating countries are EU Member States. If this is not the case, additional import requirements may have to be taken into account.

		IIT Trials								
CATE-GORY	Activity/Responsibilities	Option A Supply of blinded Patient Packs by NVS (full support)				Option B Supply of Bulk/Primary packaged unlabeled Drug product by NVS				
		TRD	CPO	NVS QPs	Spons or	TRD	CPO	NV S QPs	Supp lyCR O	Spons or
IMP CERTIFICATION	QP Batch certification of packed IMP Step 1: Manufacturer applies GMPs equivalent to EU GMPs Step 2: Compliance with Product Specification File for packed IMP (CoC level) Step 3: Compliance with approved Quality Part of IMPD for packed IMPs (CoC level), per EU country			X					CRO QP	
	Sponsor release for shipment to trial site per EU country (elements mentioned below, documentation in trial file): CTA Approval per EU country EC Approval per EU country QP Batch certification of packed IMPs				X					X
DISTRIBUTION	Procurement of Import licenses, as appropriate		X						X	
	Storage and distribution of patient packs to trial sites via country depots		X						X	
	Return and Destruction of trial medication		X						X	
	Recalls	X	X	X	X	X	X	X	X	X
	Complaints	X	X	X	X	X	X	X	X	X

		IIT Trials								
CATE-GORY	Activity/Responsibilities	Option A Supply of blinded Patient Packs by NVS (full support)				Option B Supply of Bulk/Primary packaged unlabeled Drug product by NVS				
		TRD	DRA	NVS QPs	Spons or	TRD	DRA	NVS QPs	Suppl y CRO	Spons or
CTA ACTIVITIES	Get EUDRACT number and inform involved parties (Sponsor: report to Clinical Liaison)				X					X
	(1) Provide Novartis (cross)-referencing letter and SmPC, as applicable		HQ or CPO				HQ or CPO			
	Provide QP Declaration for manufacturers in 3rd countries to Global DRA (HQ), as applicable			X				X	CRO QP	
	Provide Manufacturing Authorisations (EU Drug product manufacturing sites only) to Global DRA (restricted to sites used/involved by Novartis)	Reg CMC				Reg CM C			X	
	Provide other quality-related documents to Global DRA, as applicable (e.g., TSE certificate)	Reg CMC				Reg CM C			X	
	Provide IMPD Quality section to Global DRA, as applicable	Reg CMC				Reg CM C			X	
	Ensure publishing of the IMPD in REDI and Dispatch the Quality dossier (IMPD) and Novartis Cross-reference letter via REDI to DRA CPOs, as applicable		GI. DRA (HQ)				GI. DRA (HQ)			
	Submit IMPD Quality section to HA, referring to Sponsor's EUDRACT No., if applicable		CPO				CPO			
	Inform Sponsor QP and Global DRA about submission of IMPD Quality section, as applicable		CPO				CPO			
	Inform QPs about CTA approval (including amendments) and any relevant updates that				X (via Clinic al					X (via Clinic al

		IIT Trials								
CATE-GORY	Activity/Responsibilities	Option A Supply of blinded Patient Packs by NVS (full support)				Option B Supply of Bulk/Primary packaged unlabeled Drug product by NVS				
		TRD	DRA	NVS QPs	Spons or	TRD	DRA	NVS QPs	Suppl y CRO	Spons or
	happened during HA review (for IIT: Global DRA/REG CMC /DRA CPO also to be informed via Clinical Liaison)				Liaison)					Liaison)
	Provide IMPD Quality section to QP or delegate, as applicable		CPO				CPO			
	Provide substantial amendment IMPD Quality documentation to Global DRA, as applicable	Reg CMC				Reg CMC				
	Ensure REDI publishing of the substantial amendment IMPD documentation and Dispatch the amended Quality dossier via REDI to DRA CPO, as applicable		GID RA				GI DRA			
	Submit substantial amendments to IMPD Quality section to HA, as applicable		CPO				CPO			

(1) Novartis Cross-reference letter is provided by Global DRA for global study or DRA CPO for local study

		IIT Trials								
CATE-GORY	Activity/ Responsibilities	Option A Supply of blinded Patient Packs by NVS (full support)				Option B Supply of Bulk/Primary packaged unlabeled Drug product by NVS				
		TRD	DRA	NVS QPs	Sponso r	TRD	DRA	NVS QPs	Suppl y CRO	Spons or

CONTRACTS	Sponsor – CRO for IIT Trials for Option B	Not applicable				X	X
	Novartis QP – CRO QP for Option B	Not applicable			X	X	

ABBREVIATIONS

CoA	Certificate of Analysis	HQ	Head Quarters
CoC	Certificate of Compliance	IMP	Investigational Medicinal Product
CPO	Country Pharma Organization	IMPD	Investigational Medicinal Product Dossier
CPO-QP	CPO Qualified Person	NVS	Novartis
CTA	Clinical Trial Authorization	QA	Quality Assurance
EC	Ethic Committee	QP	Qualified Person
EU	European Union	Reg-CMC	Global Regulatory-Chemistry, Manufacturing and Control
DRA	Drug Regulatory Affairs	SmPC	Summary of Product Characteristics
GMP	Good Manufacture Practice	TRD	Technical Research and Development
HA	Health Authority	TSE	Transmissible Spongiform Encephalopathy

For more information refer to the Novartis European Union Clinical Trial Directive 2001/20/EC/Investigator Initiated Trials Website educational material

<http://www.novartisclinicaltrials.com/EUDirectiveIIT/landing.do>

